^a The investigator may utilize investigator's staff or a qualified home healthcare service provider to provide such services at the subject's home as appropriate per institutional policies, local law and regulations, and in accordance with the study laboratory manual. Home visits can be performed for visit days 8, 15, 64, 71, and 113.

^b Relative to study drug administration on day 1

^c Pregnancy test will be performed for female subjects that have had menarche and for those that experience menarche while they are on the study. Screening pregnancy test will use serum samples, but all other pregnancy assessment will be done using urine samples.

^d At PI discretion according to local guidance.

esCTX and P1NP should be taken approximately the same time (+ 1 hour) of day 1 collection time.

⁹ PI or designee should perform telephone safety assessment on day 43 (± 3 days), the assessment should include recording any adverse or serious adverse event and any concomitant medications.

^h Injection site reactions (ISR) should be evaluated at every visit, approximately 20 to 30 minutes after administration of investigational product. Confirmed ISR should be appropriately reported as adverse events.

ⁱ Echocardiogram will be performed only at screening if subject does not have prior echocardiogram performed in the last 6 months.

^j If subject discontinues from study, the EOS visit will be the same as the follow-up visit. After end of study, serious adverse events, regardless of causality, will be reported to Amgen. Please refer to Section 9.2.3 for additional details.

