7.2 General Study Procedures

Study tests and procedures will be performed only after written informed consent and subject assent (as applicable by local law) is obtained. During the study, every effort should be made to conduct study procedures as described in the Schedule of Assessments (Table 6). The investigator may utilize investigator's staff or a qualified home healthcare service provider to provide such services at the subject's home as appropriate per institutional policies, local law and regulations, and in accordance with the study lab manual.

Any missed visits, tests not done, and examinations not conducted must be reported as such on the eCRFs.

In the event that multiple procedures are required to be conducted at the same time, ECG and vital sign assessments should be performed before blood samples are drawn.

On-study bone turnover markers (BTM: sCTX and P1NP) samples should be collected approximately at the same time (\pm 1 hour) of day 1 collection time.

All blood samples should be collected at the same time at each visit.

Blood draws and safety assessments on dosing day should be performed before IP administration.

Additional procedures deemed necessary as part of standard of care or as required by local laws and regulations may be performed at the Investigator's discretion.

Acceptable windows for visits and PK and BTM sample collections:

- \pm 2 days for days 8 and 64
- \pm 3 days for days 15, 29, 57, 71, and 85
- \pm 7 days for days 113 and 169/EOS

Laboratory Assessments

For a complete listing of laboratory test panels and analytes, please refer to Section 7.4.12.

It is the responsibility of the investigator to ensure that all procedures are performed according to the protocol.

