7.3.1 Follow-up Visit(s) and End of Study Visit

Subjects will return to the clinic for follow-up visits on study days 64, 71, 85, and 113. End of study visit will occur on day 169/EOS.

Refer to the Schedule of Assessments (Table 6) for additional details.

- Physical Examination as per standard of care
- Bilateral facial nerve function examination (cranial nerve VII)
- Vital signs (ie, heart rate, respiration rate, and temperature)
- Weight and height
- ECG
- Laboratory assessments including chemistry with calcium, phosphorous, magnesium, iPTH levels, and hematology
- DXA assessments of the AP lumbar spine (DXA will not be performed on study day 113)
- Pregnancy test (urine dipstick method)
- Adverse event and serious adverse event reporting
- Documentation of concomitant medications
- Dispensation of calcium and vitamin D
- Collection of serum PK sample
- Bone turnover markers (sCTX and P1NP)
- Collection of anti-romosozumab antibody sample

If the subject discontinues the study prior to the day 169 visit, a follow-up visit will occur within 30 days of the last dose of IP or subject's last visit. All procedures outlined for the end of study visit, day 169, will be performed during this follow-up visit with the following exception: DXA scans will only be performed if > 30 days have elapsed since the previous DXA assessment.

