9. SAFETY DATA COLLECTION, RECORDING, AND REPORTING

9.1 Definition of Safety Events

9.1.1 Adverse Events

An adverse event is defined as any untoward medical occurrence in a clinical trial subject. The event does not necessarily have a causal relationship with study treatment. The investigator is responsible for ensuring that any adverse events observed by the investigator or reported by the subject after signing of the ICF through day 169/EOS visit, End of Treatment visit, or 30 days after the last dose of IP (whichever period is longer) are reported using the Events eCRF.

The definition of adverse events includes worsening of a pre-existing medical condition. Worsening indicates that the pre-existing medical condition or underlying disease (eg, diabetes, migraine headaches, and gout) has increased in severity, frequency, and/or duration more than would be expected and/or has an association with a significantly worse outcome than expected. A pre-existing condition that has not worsened more than anticipated (ie, more than usual fluctuation of disease) during the study, or involves an intervention such as elective cosmetic surgery or a medical

procedure while on study, is not considered an adverse event. Change in severity from previously reported grade to another distinct grade (in the opinion of the investigator) should be recorded on the Event eCRF. The investigator's clinical judgment is used to determine whether a subject is to be removed from treatment due to an adverse event. In the event a subject, or subject's legally acceptable representative requests to withdraw from protocol-required therapies or the study due to an adverse event, refer to Section 8.1 for additional instructions on the procedures recommended for safe withdrawal from protocol-required therapies or the study.

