9.2.2 Reporting Procedures for Serious Adverse Events

The investigator is responsible for ensuring that all serious adverse events observed by the investigator or reported by the subject that occur after signing of the informed consent through day 169/EOS visit, ET visit, or 30 days after the last dose of IP (whichever period is longer) are reported using the Events eCRF. All serious adverse events must be submitted to Amgen **immediately and no later than** 24 hours following the investigator's knowledge of the event via the Events eCRF.

If the electronic data capture (EDC) system is unavailable to the site staff to report the serious adverse event, the information is to be reported to Amgen via a paper Serious Adverse Event Contingency Report Form (also referred to as the electronic Serious Adverse Event [eSAE] Contingency Report Form) **immediately and no later than** 24 hours of the investigator's knowledge of the event. See Appendix B for a sample of the Serious Adverse Event Worksheet/eSAE Contingency Report Form. For EDC studies where the first notification of a Serious Adverse Event is reported to Amgen via the eSAE Contingency Report Form, the data must be entered into the EDC system when the system is again available.

The investigator must assess whether the serious adverse event is possibly related to the investigational product. This relationship is indicated by a "yes" or "no" response to the question: Is there a reasonable possibility that the event may have been caused by the investigational product? Relatedness means that there are facts or reasons to support a relationship between investigational product and the event.

The investigator must assess whether the adverse event is possibly related to other protocol-required therapies. This relationship is indicated by a "yes" or "no" response to the question: Is there a reasonable possibility that the event may have been caused by other protocol-required therapies? Relatedness means that there are facts or reasons to support a relationship between investigational product and the event.

The investigator must assess whether the adverse event is possibly related to any study mandated activity (including any screening procedure[s]). This relationship is indicated by a "yes" or "no" response to the question: "Is there a reasonable possibility that the event may have been caused by a study activity and/or procedure"?

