5.1 Basic Definitions

Treatment-emergent Adverse Events (TEAE)

Adverse Events (AEs) starting on or after first dose of investigational product as determined by the flag indicating if the adverse event started prior to the first dose on the Adverse Events eCRF and up to the end of study date.

Treatment-emergent Serious Adverse Event (TESAE)

Treatment-emergent adverse events indicated as serious on the Events eCRF

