5.3 Study Dates

Informed Consent Date

The date on which a subject signed the informed consent.

Enrollment Date

The date of enrollment in eCRF.

First Dose Date

The date of administration of the first dose of IP.

Last Dose Date

The date of administration of last dose of IP

End of the Treatment Period Date

The end of the **second** treatment period date is defined as the date of the last assessment at the **second** visit. For subjects who discontinue from the study before completing the **second** visit, the end of study date is used for the end of the **second** treatment period end date. For those subjects who missed the **second** visit but did not terminate the study early, the target day **second** plus 3 days will be used as the end of the **second** treatment period date.

Start of the Follow-up Period Date

The start of the follow-up period date is defined as the end of the **sector** treatment period date plus one day.

End of the Follow-up Period Date

For subjects with non-missing start of the follow-up period date, the end of the follow-up period date is defined as the end of study date as recorded on the electronic case report form (eCRF).

End of Study Date

The date recorded on the End of Study electronic case report form (eCRF)

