9.6 Safety Analyses

9.6.1 Adverse Event

The Medical Dictionary for Regulatory Activities (MedDRA) version 25.0 or later will be used to code all events categorized as adverse events to a system organ class and a preferred term.

The subject incidence of adverse events will be summarized for all treatmentemergent adverse events, serious adverse events, adverse events leading to withdrawal of

investigational product, fatal adverse events, and adverse events of interest. The severity grade of all treatment-emergent

adverse events will be summarized based on Severity Intensity Scale for Adverse Events.

Subject incidence of all treatment-emergent adverse events, serious adverse events, adverse events leading to withdrawal of investigational product, and fatal adverse events will be tabulated by system organ class and preferred term in descending order of frequency. Subject listing of all treatment-emergent adverse events will also be provided.

Subject incidence of events of interest (EOI; standardized MedDRA queries and/or Amgen customized queries) will also be summarized according to their categories and preferred term. Events of interest of hypersensitivity and malignancy will be identified using a narrow search/scope in standardized MedDRA queries (SMQ). Event of interest of hypocalcemia, injection site reaction, hyperostosis and osteoarthritis will be identified using Amgen-defined MedDRA search strategies. **Serious cardiovascular adverse events will be identified using cardiac and vascular system organ class (SOC) in MedDRA.** Adjudicated-positive adverse events of osteonecrosis of the jaw (ONJ) will also be summarized as EOIs.

The number and percentage of subjects reporting adverse events will be evaluated for each dose cohort, across dose cohorts, and will also be tabulated by relationship to study drug. In addition, summary of cranial nerve examination at each visit and the result change from entry exam over time for each cohort will be tabulated.

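### The SAP closes the treatment-emergent window at the subject's end of study date, but the protocol collects adverse events to 30 days after the last dose when that is later

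*SAP*

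**What the plan says.** **SAP.** Section 5.1 defines a treatment-emergent AE by a start flag and a cutoff, ending "prior to the first dose on the Adverse Events eCRF and up to the end of study date". Treatment-emergent SAEs are defined as a subset of these, so they inherit the cutoff. Section 5.3 defines the end of study date as "The date recorded on the End of Study electronic case report form (eCRF"). Section 9.6.1 tabulates treatment-emergent AEs by system organ class and preferred term, summarises their severity, and adds: "Subject listing of all treatment-emergent adverse events will also be provided". Section 10 lists one change from the protocol, the dropped laboratory grade shifts. It does not mention the AE window.

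**Protocol.** Section 9.1.1 has AEs reported from signing of the consent form "through day 169/EOS visit, End of Treatment visit, or 30 days after the last dose of IP (whichever period is longer"). Section 9.2.1 repeats the rule for non-serious events. Section 9.2.2 does so for SAEs: "through day 169/EOS visit, ET visit, or 30 days after the last dose of IP (whichever period is longer) are reported using the Events eCRF".

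For a subject who leaves early, Section 7.3.1 says that "a follow-up visit will occur within 30 days of the last dose of IP or subject's last visit". A footnote to the Schedule of Assessments (Table 6) adds: "If subject discontinues from study, the EOS visit will be the same as the follow-up visit".

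**The concern.** The clause that takes the longest period in the protocol matters only when 30 days after the last dose falls after the subject's final visit. The SAP has no counterpart to it. In that situation sites must enter events on the Events eCRF that the SAP's main safety definition then excludes, and the SAP does not declare this as a departure.

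Safety and tolerability are a secondary objective and treatment-emergent AEs a secondary endpoint. Cohorts have four subjects, so one event can change how a dose level looks. The AE listing is itself limited to treatment-emergent events, so it would not show an event that the cutoff had removed.

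**Working it through.** The documents give no figure to reproduce on this point. The check is date arithmetic.

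**Step 1. Whose end of study date?** Protocol 3.5.2 defines end of study for the whole trial, as last subject last visit. If the SAP meant that date, there would be no gap. SAP 5.3 instead takes the date from the End of Study eCRF, and uses it to close the treatment period of an individual who discontinues early. It is therefore a subject-level date.

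**Step 2. Formula.** Days that are collected but not treatment-emergent = max(0, last dose day + 30 − end of study day).

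**Step 3. Completers.** Protocol 7.2 allows "7 days for days 113 and 169/EOS" either side of target, so the earliest EOS is day 169 − 7 = 162. A gap would need a last dose after day 162 − 30 = 132. Dosing days are redacted, but the synopsis starts follow-up from day 64.
- Assumed last dose on day 57: 57 + 30 = 87, before 162, gap 0.
- Assumed last dose on day 88, later than is plausible: 88 + 30 = 118, before 162, gap 0.

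Subjects who stop drug but remain on study to day 169 also have no gap, because their last dose is earlier still.

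**Step 4. Subjects who leave the study early.** The exit visit counts as the EOS visit and falls within 30 days of the last dose or of the last visit. It can come before or after the 30-day point.

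| End of study date, days after last dose | Days collected but not treatment-emergent |
|---|---|
| 0 | 30 |
| 7 | 23 |
| 14 | 16 |
| 21 | 9 |
| 29 | 1 |
| 30 or more | 0 |

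**Step 5. Which leavers can have later events in the database?** Protocol 8.3.2 gives four reasons for removal from study.
- Death: no later events.
- Loss to follow-up: normally none reported.
- Withdrawal of consent: Protocol 8.1 includes subject data only up to that point, apart from publicly available data where permitted.
- Sponsor decision: no such limit, so later events can be reported up to 30 days after the last dose.

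**Step 6. Effect on incidence.** SAP 5.6 counts a subject once per event. An omission therefore changes a row only if that subject has no earlier event in it. The change is then 1/n.
- Cohort of 4: 1/4 = 25 points.
- Cohort of 5, if the leaver is replaced under Protocol 3.4 and both are counted: 1/5 = 20 points.
- All 16 subjects: 1/16 = 6.25 points.
- All 24 subjects: 1/24 = 4.2 points.

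**Step 7. After the change.** If the window ends at the later of the two dates, the formula gives 0 for every subject whose data may be used.

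**The case against.** The strongest reply is that the affected group is nearly empty. Three of the four routes out of the study leave few or no usable later events. A subject with a tolerability problem is expected to stop treatment, not leave the study: adverse events appear among the reasons for removal from treatment (Protocol 8.3.1) but not from study (8.3.2), and 8.1 urges that such subjects remain on study. For early leavers the exit visit may also fall at or after 30 days from the last dose, and the documents do not say how the End of Study eCRF date is completed for them. This is a descriptive phase 1b trial with a pharmacokinetic primary endpoint. All of this stands, and it keeps the point minor. It does not remove the conflict, because removal by sponsor decision remains open and Protocol 3.4 foresees subjects withdrawn with too little follow-up after dosing.

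Protocol 9.2.3 might also be cited, since it requires no SAE monitoring after the reporting period or after end of study. It does not cancel the 30-day reporting rule in 9.2.2.

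A reader might infer that every AE, SAE and event-of-interest table is cut short. SAP 9.6.1 does not support that. It names serious, fatal and of-interest events without consistently attaching the treatment-emergent qualifier, so the reach of the cutoff in those tables is unclear.

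**Conclusion.** The SAP and protocol windows conflict in their current text, and nothing else in the SAP closes the gap. The consequence is certain only for the TEAE and treatment-emergent SAE summaries and the TEAE listing. It arises only when a subject leaves the study less than 30 days after a dose, later events are still reported, and one of them starts after the end of study date. The gap is then between 1 and 30 days; 30 is the extreme, with an end of study date on the day of dosing. The 25-point shift holds only for a 4-subject cohort and a subject with no earlier event in that row. If no such departure occurs, the effect is zero.

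A reader might go further and conclude that the safety summary is biased towards fewer events because early leavers tolerate the drug poorly. The omission can only remove events, so that direction is possible. The documents give no evidence that leavers of this kind have more events, and the protocol tries to keep subjects with adverse events on study. The case for the change rests on the mismatch alone.

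**What to change.** In SAP 5.1, end the treatment-emergent window at *the later of the end of study date and 30 days after the last dose of IP*, and state that data after withdrawal of consent remain excluded as in Protocol 8.1. While editing, say in SAP 9.6.1 whether the serious, fatal and event-of-interest tables are limited to treatment-emergent events. If the narrower window is intended, declare and justify it in SAP Section 10 instead.

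The cost is one phrase in 5.1 and a clarifying sentence in 9.6.1. No new data are needed, because the protocol already requires these events on the Events eCRF.

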5.2 Study Points of Reference

Baseline

The baseline measurement is defined as the last measurement prior to the first dose of IP. If the measurement is taken on the same day as the first dose and the exact measurement time relative to the first dose is unknown, it will be assumed to have been taken prior to the first dose of IP. If a subject does not receive IP, baseline is the closest recorded measurement on or prior to the enrollment date.

Note: If baseline result from DXA assessment is not available, the results assessed on or before Study Day 14 will be considered baseline.

Study Day 1

Day 1 is defined as the first day that investigational product is administered to the subject. The day before Day 1 is referenced as Day -1.

Study Day

Post day of dose: study day= (study date - date of study Day 1) +1

Pre day of dose: study day= (study date – date of study Day 1)

The day prior to the first investigational product dosing is Day -1 while the day of the first investigational product dose is Day 1.

Analysis Visit

To allow for variations in scheduling study visits, the analysis visit windows defined in Appendix A will be used to assign evaluations to the most appropriate nominal visit for analysis and summarization.

5.3 Study Dates

Informed Consent Date

The date on which a subject signed the informed consent.

Enrollment Date

The date of enrollment in eCRF.

First Dose Date

The date of administration of the first dose of IP.

Last Dose Date

The date of administration of last dose of IP

End of the Treatment Period Date

The end of the **second** treatment period date is defined as the date of the last assessment at the **second** visit. For subjects who discontinue from the study before completing the **second** visit, the end of study date is used for the end of the **second** treatment period end date. For those subjects who missed the **second** visit but did not terminate the study early, the target day **second** plus 3 days will be used as the end of the **second** treatment period date.

Start of the Follow-up Period Date

The start of the follow-up period date is defined as the end of the **sector** treatment period date plus one day.

End of the Follow-up Period Date

For subjects with non-missing start of the follow-up period date, the end of the follow-up period date is defined as the end of study date as recorded on the electronic case report form (eCRF).

End of Study Date

The date recorded on the End of Study electronic case report form (eCRF)

5.4 Study Time Intervals

Screening Period

The time period between the date of informed consent and first dose of IP.

On-Study Period

The time period from the enrollment date to the end of study date, inclusive.

Treatment Period

The time period from the first dose date to the end of the **sector** treatment period date Inclusive.

Follow-up Period

For subjects entering in the **control** follow-up period: the time period from the start of follow-up period date to the end of study date, inclusive.

5.5 Subject Disposition

Enrolled

Individuals are considered enrolled when the investigator confirms that the subject has met all eligibility criteria (both screening and day 1 pre-dose assessments). Enrolled individuals are referred to as "subjects".

Exposed to IP

Subjects are considered exposed to IP if they have a value for the sum of IP volume that exceeds zero.

